9.3 SAMPLE SIZE CALCULATIONS

A two-sided logrank test with an overall sample size of 225 subjects (113 in the control group and 112 in the treatment group) achieves 86.1% power at a 0.05 significance level to detect a hazard ratio of 1.74 when the proportion of wounds healed in the control group is 0.5. The study lasts for 12 weeks with all subjects beginning the study together (no accrual periods). The proportion dropping out of the control group is 0.033 per week. The proportion dropping out of the treatment group is 0.0083 per week. The proportion switching from the control group to another group with a hazard ratio equal to that of the treatment group is 0.

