3 STUDY OUTCOMES

Primary outcome measure is time to heal in patients treated with epidermal grafting and SOC vs. SOC alone (**Group 1A** versus **Group 2A** at 6 weeks; and **Group 1A** versus **Group 2B** at 12 weeks).

Secondary outcomes include:

1. Percentage of wounds closed at 6 and 12 weeks.
2. Correlation between protease activity and healing at 4 and 8 weeks.
3. Incidence of adverse events at 12 weeks.
4. Pain reduction between baseline and 12 weeks.
5. Cost-effectiveness (see Appendix 19.4)
6. Cost-benefit (see Appendix 19.4)

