5 STUDY POPULATION

5.1 NUMBER OF SUBJECTS

The study will consist of up to 30 centers in the United States each contributing about 10 subjects per center in order to obtain 300 evaluable subjects. We anticipate a 10% drop out rate during the trial for both Groups 1A and Group 2A, and 30% of subjects in Group 2A will switch to Group 2C and therefore a total of 225 subjects will be recruited. This trial employs an adaptive design therefore the enrollment numbers may be reduced or increased based on planned interim analysis.

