9.6 INTERIM ANALYSIS

One interim safety and efficacy analysis will be performed when approximately 110 subjects have been enrolled (approximately 50% of subjects). The total number of AEs and SAEs will be calculated, and the proportion of healed wounds tabulated for all groups (at 12 weeks). New sample size calculations will be performed based on the proportion of healed wound data (time to heal). No statistical analysis will be conducted.

TRIAL STOPPING RULES

The Medical Monitor may unblind, or appoint an independent assessor to unblind interim data analyses to determine whether the study should be stopped if any of the following occur:

- If the primary outcome likely has reached statistical significance and there is agreement to analyze the secondary outcomes regardless of whether they are likely to achieve statistical significance or not.
- If the primary outcome has likely not reached statistical significance and based on futility boundary analysis, the numbers of additional subjects needed to reach significance based on the rate data are too high to realistically extend the trial.
- $\geq 25\%$ of ulcers have deteriorated (meaning an increase in area from baseline to 12 weeks).
- A significant proportion of patients ($> 25\%$) in either group continue to experience infections despite Prisma/antimicrobial treatment or other measures
- Excessive non-planned withdrawal of subjects

List of variables for interim analysis

- Site ID
- Subject ID
- Treatment assignment
- Gender
- Pain score at baseline and 12 weeks
- Wound healed (Y/N) by 12 weeks (after 12 weeks have elapsed from date of randomization)
- When wound healed (days from randomization)
- Ulcer area at baseline and 6/12 weeks
- AEs (by category; have separate category for infected wounds) and SAEs at 12 weeks (count by subject, and description/category where applicable)
- Withdrawn subjects or subjects that have been lost to follow-up (count and by assignment with reason where applicable)
- Number of subjects in **Groups 2B and 2C**.

PATIENT POPULATIONS

The populations defined for the final analysis will include the intent-to-treat (ITT), per protocol (PP), and safety populations.

INTENT-TO-TREAT POPULATION

The ITT population will be analyzed for primary and secondary endpoints up to 12 weeks; however, Index Ulcers that have been healed are still subject to confirmed wound closure for 2 weeks later (up to 14 weeks for ulcers initially healed in the 12th week).

PRE PROTOCOL POPULATION

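### Section 5.1 asks for 300 evaluable subjects from 225 recruited, and section 9.3 gives no power for the 6-week primary test and counts Group 2C switchers as non-informative loss over 12 weeks

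*Combined protocol and SAP*

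**What the plan says.** Section 5.1 describes up to 30 centers, "each contributing about 10 subjects per center in order to obtain 300 evaluable subjects". It then expects 10% dropout in Groups 1A and 2A and continues: "30% of subjects in Group 2A will switch to Group 2C and therefore a total of 225 subjects will be recruited". It adds that "the enrollment numbers may be reduced or increased based on planned interim analysis".

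Section 9.3 takes 113 control and 112 treated subjects, 12 weeks of follow-up, no accrual period and 50% healed on control, and reports that the design "achieves 86.1% power at a 0.05 significance level to detect a hazard ratio of 1.74". On losses it says: "The proportion dropping out of the control group is 0.033 per week". The treatment rate is 0.0083 per week, and switching to a group with the treatment hazard is set to 0.

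Section 3 makes time to heal primary for "Group 1A versus Group 2A at 6 weeks; and Group 1A versus Group 2B at 12 weeks". Section 9.2 repeats both comparisons and acts if either is significant. Sections 4 and 6.3 form Group 2C at TV7 from controls whose area reduction is below 40%.

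Section 9.6 places the interim look "when approximately 110 subjects have been enrolled (approximately 50% of subjects"), and says: "New sample size calculations will be performed based on the proportion of healed wound data (time to heal"). It does not say which comparison that recalculation serves.

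**The concern.** There are three linked problems.

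- Losses can only reduce a recruited number, so 300 evaluable cannot come from 225 recruited. Sites and the IRB read section 5.1 for the size of the trial.
- One of the two primary tests has no power statement. It is also the only one that compares everyone as randomised, because Group 2B is what remains of the control arm after poor responders have left.
- The one stated power treats switchers as loss that is spread evenly and unrelated to healing. The plan moves them all at one visit because they are healing badly. A reader who takes 86.1% as the power of 1A versus 2B relies on an assumption that section 9.3 does not state.

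**Working it through.** **Evaluable numbers from 225 (section 5.1 losses).**
- 10% dropout in both arms: 225 × 0.9 = 202.5.
- Groups 1A plus 2B, control losses added: 112 × 0.9 + 113 × 0.6 = 100.8 + 67.8 = 168.6.
- Groups 1A plus 2B, control losses in sequence: 112 × 0.9 + 113 × 0.9 × 0.7 = 100.8 + 71.2 = 172.0.

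**Which number is the pre-loss one.** Section 9.3 applies weekly loss to 113 + 112 = 225. For section 9.6, 110/225 = 49%, against 110/300 = 37%. Both sections agree with the 225 recruited in 5.1.

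**Where 0.033 comes from.** 0.033 × 12 = 0.396, which is 5.1's 0.10 + 0.30. For treatment, 0.0083 × 12 = 0.0996, which is the 10% dropout alone.

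**Reproducing 86.1%.** Control hazard λ = ln 2/12 = 0.0578 per week; treatment hazard 1.74 × λ = 0.1005. With loss rate e, expected events = n × λ/(λ + e) × [1 − exp(−(λ + e)T)].
- Control, e = 0.033, T = 12: 47.7. Treatment, e = 0.0083: 75.4. Total D = 123.1.
- Power (Schoenfeld) = Φ(√(D/4) × ln 1.74 − 1.960) = Φ(3.073 − 1.960) = 86.7%.
- A Lakatos-type stepwise calculation gives 85.8%, and Freedman's formula 85.0%. The stated figure stands on its own inputs.

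**The 6-week test, 1A versus 2A.** Same hazard ratio from week 0, constant hazard (assumption) and loss of 0.0083 per week in both arms, since no one has yet switched.
- Healed by week 6: control 1 − 0.5^0.5 = 29%; treatment 1 − 0.5^0.87 = 45%.
- Events: 32.3 + 49.6 = 81.9.
- Power at 0.05: Φ(2.507 − 1.960) = 71%.
- Power at 0.025: Φ(2.507 − 2.241) = 60%. This threshold applies if section 9.7's Hochberg procedure covers only the two primary tests and the other one fails.

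The hazard shape is not given, so I varied it with cumulative hazard ln 2 × (t/12)^k in controls:

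| Weibull k | Events by week 6 | Power at 0.05 |
|---|---|---|
| 0.75 | 93.7 | 76–77% |
| 1 | 81.9 | 71% |
| 1.25 | 71.2 | 65% |
| 1.5 | 61.7 | 58–59% |
| 2 | 45.6 | 46% |

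**The 12-week test, 1A versus 2B (illustration only).** Log-rank simulation with 4,000 runs per cell, weekly visits, constant hazard, dropout of 0.0083 per week, and 34 of 113 controls (30%) moved at week 6 and censored there.
- Switchers a random pick of unhealed controls: about 84%.
- Switchers of whom 0, 10, 20 or 30% would have healed by week 12 on SOC: about 37, 54, 71 and 81%.

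For reference, an average control unhealed at week 6 would heal by week 12 with probability 1 − exp(−ln 2/2) = 29%. The documents give no healing rate for switchers and no rule for handling Group 2C.

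**The case against.** The strongest reply is that the plan is sounder than it looks. The recruited number is 225 in 5.1, 9.3 and 9.6, and it can be met. The 300 may simply be 30 centers times 10. The 0.033 can be derived from 5.1, so the planner did allow for switchers. The size can change at the interim. Section 9.2 needs only one primary test to succeed: in a further simulation with switchers censored, the chance of at least one significant result was about 71 to 87% unadjusted, or 61 to 82% with a two-test Hochberg, when 0 to 30% of switchers would have healed on SOC.

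Much of this stands, and it rules out several stronger readings:

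- A reader might infer that enrolment cannot be met. Only the 300 evaluable fails.
- A reader might infer that the labels were swapped, since 150 × 0.9 + 150 × 0.6 = 225. Sections 9.3 and 9.6 treat 225 as the number before loss, so the documents do not support this. Only the sponsor could confirm it.
- A reader might infer that 86.1% is miscalculated. It is not.
- A reader might infer that the plan censors Group 2C at week 6. Section 9.7 censors missing data only and does not name 2C, and these subjects continue weekly visits.
- A reader might infer that the 12-week test has almost no power. Simulated figures run from about 4% (2C excluded from baseline, none would have healed) to about 90% (2C censored, 40% would have healed). That spread reflects inputs that the documents do not give, so it is not a finding about the plan.

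The reply does not supply the power of the 6-week test or state the non-informative loss assumption. The re-estimation names no comparison, so it cannot be said to protect either test.

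**Conclusion.** The point holds in three limited parts.

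1. 300 evaluable from 225 recruited is impossible. The 300 is the figure to correct unless the sponsor confirms another meaning.
2. The 6-week primary test has no stated power. With 225 subjects it is about 71% at 0.05, and 46 to 77% across the shapes tried. This rests on a hazard ratio of 1.74 from week 0, 50% control healing at week 12 and 10% dropout. Every value is below the only power the plan states.
3. The 86.1% is arithmetically right but assumes non-informative loss of switchers. It cannot be carried over as the power of 1A versus 2B when leaving depends on poor healing. The direction is clear if switchers heal less well than the average unhealed control; the size cannot be fixed from the documents.

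Selection in the 1A versus 2B comparison is a separate design matter, which restating power does not cure.

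**What to change.** - **5.1:** state 225 recruited with the evaluable numbers it yields (about 202 completers; about 169 to 172 in 1A plus 2B). If the sponsor confirms that 300 had another meaning, redo 9.3 and the 50% in 9.6.
- **9.3:** say that 86.1% refers to a 12-week comparison in which switchers count as non-informative loss within the 0.033 per week, and that it does not hold as the power of 1A versus 2B when switching depends on poor healing. Add the 6-week power with its hazard and alpha assumptions.
- **9.2 or 9.7:** state how Group 2C enters the 12-week test. Recompute the 12-week power under that rule, labelled as illustrative with its switcher-healing assumption.
- **9.6:** name the comparison that the sample size re-estimation serves.

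The cost is a less favourable stated power. No patients are added and the primary analysis is unchanged. Accepting about 71% at 6 weeks becomes an explicit sponsor decision; under a constant hazard, 80% would need 103 events, or 103/(81.9/225) ≈ 283 randomised.

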9.2 RESEARCH HYPOTHESES

Primary endpoints

H1: Time to heal

Time to heal after 12 weeks of CelluTome™ + SOC (**Group 1A**; maximum of 3 CelluTome™ applications) versus 12 weeks of SOC (**Group 2B**) will be equal for both groups or time to heal after 6 weeks of CelluTome™ + SOC (**Group 1A**; maximum of 2 CelluTome™ applications) versus 6 weeks of SOC (**Group 2A**) will be equal for both groups. Formally, $H_0: T_1 - T_2 = 0$; $H_A: T_1 - T_2 = D_1 \neq 0$, where T_1 is the time to heal for **Group 1A**, T_2 is the time to heal for **Group 2A or 2B** depending whether T_2 is 12 or 6 weeks, D_1 is the difference ($T_1 - T_2$) assuming the alternative hypothesis, and statistical test used is log rank applied to a Kaplan-Meier analysis. If either result is statistically significant, results will be adjusted using Cox regression and appropriate covariates.

Secondary endpoints

H2: Proportion of wounds healed

The proportion of wounds healed at 12 weeks after 12 weeks of CelluTome™ + SOC (**Group 1A**; maximum of 3 CelluTome™ applications) versus 12 weeks of SOC (**Group 2B**) will be equal for both groups. Formally, $H_0: P_1 - P_2 = 0$; $H_A: P_1 - P_2 = D_1 \neq 0$, where P_1 is the proportion of wounds healed for **Group 1A**, P_2 is the proportion of wounds healed for **Group 2B**, D_1 is the difference ($P_1 - P_2$) assuming the alternative hypothesis, and statistical test used is chi square.

H3: Incidence of Adverse Events (AEs)

The incidence of adverse events (AEs) by 12 weeks after 12 weeks of CelluTome™ + SOC (**Group 1A**; maximum of 3 CelluTome™ applications) versus 12 weeks of SOC (**Group 2B**) will be equal for both groups. Formally, $H_0: I_1 - I_2 = 0$; $H_A: I_1 - I_2 = D_1 \neq 0$, where I_1 is the incidence of AEs for **Group 1A** on a per subject basis, I_2 is same metric for **Group 2B**, D_1 is the difference ($I_1 - I_2$) assuming the alternative hypothesis, and statistical test used is the Mann-Whitney test.

H4: Correlation of wound area with protease activity at 4 weeks

The Pearson correlation coefficient (or Spearman's rho in the case of severe non-normality) calculated

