- SAE (Poisson distribution variable, count at patient level; date of onset; resolution; brief description)

ADJUSTMENT FOR FEWR

Adjustment to control for the family wise error rate (FEWR) (also known as multiplicity of testing) will use the Hochberg step-up procedure thus: Let $p_1 \geq p_2 \geq \dots \geq p_K$ be the ordered p-values and H_1, H_2, \dots, H_K be the corresponding null hypotheses. Reject H_k and all H_j for $j \leq k$ if $p_k \leq \alpha/k$. The adjusted p-values are $p_{adj,k} = \min \{p_1, 2p_2, \dots, kp_k\}$ for $k = 1, 2, \dots, K$.

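### The 86.1% power in section 9.3 is for one log-rank test at 0.05; it allows for neither the second primary test nor the Hochberg adjustment, whose family section 9.7 leaves undefined

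*Combined protocol and SAP*

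**What the plan says.** Section 9.3 describes a single two-sided log-rank test on 225 subjects, 113 control and 112 treatment, which "achieves 86.1% power at a 0.05 significance level to detect a hazard ratio of 1.74". Control healing is taken as 0.5, follow-up is 12 weeks without accrual, and weekly losses are 0.033 (control) and 0.0083 (treatment). The section mentions no multiplicity and gives no power for a 6-week test.

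Sections 3, 9.2 (H1) and 9.7 define two primary time-to-heal comparisons: Group 1A against 2A at 6 weeks, and 1A against 2B at 12 weeks, each by log-rank. H1 joins them with an 'or' and adds: "If either result is statistically significant, results will be adjusted using Cox regression and appropriate covariates".

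Section 9.7 ends: "Adjustment to control for the family wise error rate (FEWR) (also known as multiplicity of testing) will use the Hochberg step-up procedure". It gives the procedure for K ordered p-values, but neither the value of K nor the hypotheses that form the family. Section 9.2 lists H1 to H8, of which H3 and H8 concern adverse events. Because H1 carries two tests, that is nine p-values.

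**The concern.** A power figure should belong to the rule that decides the trial. Here the stated power assumes one test at 0.05, while the SAP plans two primary tests and a family-wise correction of unstated reach.

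If the correction covers H1, a primary p-value may have to meet a threshold below 0.05, and the power falls. If it covers H2-H8 as well, null results on protease, pain or adverse events can cost the trial its primary claim, and an adverse-event difference may be held to a stricter threshold. If it does not cover H1, the power survives, but two chances at 0.05 exceed the nominal error rate. With the family undefined, the choice could be made after the results are known.

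**Working it through.** **Inputs from section 9.3:** 113 control and 112 treatment; control healing 0.5 at 12 weeks; hazard ratio 1.74; weekly loss 0.033 and 0.0083. **Assumptions not in the documents:** exponential healing times, a hazard ratio constant from week 0 to 12, and a range of effects for H3-H8.

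**1. Reproduce 86.1%.**
- Healing hazards: control ln 2/12 = 0.0578 per week; treatment 1.74 × 0.0578 = 0.1005.
- Loss hazards: -ln(1 - 0.033) = 0.0336; -ln(1 - 0.0083) = 0.0083.
- P(observed healing by week t) = λ/(λ+η) × [1 - exp(-(λ+η)t)]. At 12 weeks: control 0.421, treatment 0.673.
- Expected events: 113 × 0.421 + 112 × 0.673 = 47.6 + 75.4 = 123.0.
- Schoenfeld: √123.0 × ln 1.74 / 2 = 3.07; power Φ(3.07 - 1.96) = 86.7%.
- A Lakatos-type calculation gives an expected Z of 3.03 and power of 85.7%. Patient-level simulation (15,000 trials) gives 86.2%.

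So 86.1% is right for a single test at 0.05.

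**2. Two primary tests, standard Hochberg (K = 2).** A test wins if both p-values are at most 0.05, or if its own is at most 0.025. In the simulation the 6- and 12-week statistics correlate at about 0.80, and the 6-week test alone has about 69% power.
- Either test: about 82% (81.8%).
- 12-week test: about 81% (81.1%).
- Floor for the 12-week test, from the expected Z implied by 86.1%: Φ(3.045 - 2.241) = 78.9%.

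**3. All nine p-values (K = 9).** H2 is simulated jointly with H1. H3-H8 are independent, with a common expected Z.

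| Expected Z of each of H3-H8 | Either primary | 12-week test |
|---|---|---|
| 0 (null) | 63.9% | 61.9% |
| 1 | 64.3% | 62.3% |
| 2 | 67.3% | 65.4% |
| 2.8 (about 80% power each) | 73.5% | 72.4% |

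A cruder normal-approximation run gives 63.0% and 70.9% for either primary at the two ends, and a separate 3,000-trial simulation gives 64.7% at the null end. Hence about 63-65% rising to about 71-74%. The floor at 0.05/9 for the 12-week test is Φ(3.045 - 2.773) = 60.7%.

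**4. H1 uncorrected.** The 12-week test keeps about 86%, and at least one of the two is significant in about 88% of trials. Under the null, expected events are 113 × 0.2668 + 112 × 0.2861 = 62.2 at 6 weeks and 113 × 0.4211 + 112 × 0.4785 = 101.2 at 12 weeks. The correlation is then √(62.2/101.2) = 0.78, and the chance that at least one test reaches 0.05 is 7.9%.

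**5. The printed rule.** Section 9.7 orders p-values from largest to smallest, then rejects H_j for j ≤ k when p_k ≤ α/k. With that ordering, Hochberg rejects j ≥ k. The printed sentence would reject the hypotheses with the *larger* p-values, and it conflicts with the adjusted p-values given beside it. Steps 2 and 3 use the standard form.

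**The case against.** Four objections have force.

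- **The family is not stated.** A reader might infer that the plan's own rule caps power at 82%, or that all of H1-H8 are in the family because section 9.7 writes H_1 to H_K. The documents support neither. In section 9.7, H_1 is whichever hypothesis has the largest p-value, which is generic notation. If the adjustment covers only secondary endpoints, the 12-week test keeps about 86%. Nor is 82% a ceiling when K = 2: a stronger early effect would raise it. By the same token, H3 and H8 are not excluded from the family, but they are not placed in it either.
- **The lowest figures need null secondaries.** The 63-65% holds only if H3-H8 carry little or no effect.
- **'Either' is not a stated success criterion.** In H1 it triggers the adjusted Cox analysis. The error rate of about 8% applies only if success is claimed on either test.
- **There is no arithmetic error in section 9.3.** Its figure is correct for the conditions it states. Sections 5.1 and 9.6 also foresee changing the sample size after an interim look, so 225 is provisional.

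All four stand, and they limit what can be claimed. They do not supply the missing family, and no reading makes section 9.3 a description of the two-test primary analysis with 5% error control.

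**Conclusion.** The concern holds as a gap between the power statement and the multiplicity plan. The 86.1% is correct for one log-rank test at 0.05, and the trial plans two primary tests plus an adjustment of undefined reach. Depending on the reading, power is about 82% for either test and 81% at 12 weeks (primary family only); about 63-65%, rising to 71-74%, for either primary (all nine p-values); or about 86% at 12 weeks with about 8% type I error for an either-test claim (H1 uncorrected).

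These figures rest on section 9.3's inputs, a constant hazard ratio and standard Hochberg, and they treat controls as section 9.3 does. They may be optimistic: if a random 30% of controls (the switching share in section 5.1) are left out of the 12-week test, power for either falls to about 79% (K = 2) or 58% (K = 9, H3-H8 null).

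**What to change.** **In section 9.7:**
- Make the primary tests their own family at 0.05, by Hochberg with K = 2 or by a fixed sequence that starts with one named time point. Secondary and safety results then cannot alter the primary decision.
- Apply Hochberg to the secondary efficacy hypotheses only after a primary success.
- Report H3 and H8 outside the family, with unadjusted confidence intervals.
- Correct the index: with p-values ordered largest to smallest, if p_k ≤ α/k, reject H_j for j ≥ k.

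**In section 9.3,** restate power for the rule chosen. For K = 2 that is about 82% for either test and about 81% at 12 weeks.

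If 12 weeks is tested first at the full 0.05, 86.1% may stay only if that test compares 1A with all randomized 2A subjects as section 9.3 models them. It does not apply to Group 2B, which drops controls with less than 40% area reduction at week 6. Section 9.3 keeps 113 controls, and its loss rate matches drop-out plus switching from section 5.1: (10% + 30%)/12 = 3.3% per week. If none of the 30% who switch would have healed, healing in 2B would be 0.50/0.70 = 71%, against a modelled 1 - 0.5^1.74 = 70% in the treatment arm.

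**Cost:** SAP wording only, to be settled before results are seen. Either the stated power is slightly lower, or the second time point can be claimed only after the first.

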9.4 RANDOMIZATION

Randomization will be stratified by age of wound at the first screening visit (1-6 months and > 6 months).

The randomization algorithm will employ blocks of 2 and 4, with random selection of block sizes (Pass 11).

